Viral shedding will be summarized by the number and percentage of subjects in each challenge dose group with positive qualitative and/or quantitative RT-PCR each day from Day 2 through the end of the challenge period (Day 8 or later, in the case of a subject not meeting discharge criteria on Day 8) excluding safety results reported after receipt of antiviral therapy. The probability of viral shedding at any point during the challenge (i.e., incidence) will be estimated along with the associated exact 95% CI, separately by challenge dose group. Peak viral shedding will be calculated for each subject as the maximum shedding from Day 2 through Day 8 or discharge, and total viral shedding will be calculated via the area under the curve (AUC) with study day on the x-axis and shedding on the y-axis. These will be calculated separately for quantitative RT-PCR and quantitative culture. Mean peak and total shedding based on the AUC will be calculated for each group along with 95% CIs, and comparisons will be made as described for continuous variables in Section 9.5.1. A Wilcoxon signed-rank test will be used to compare distributions of these variables between quantitative RT-PCR and quantitative culture across all subjects, to assess if these methods of viral quantification are consistent. Scatterplots will also be presented, along with Spearman rank-order correlation estimates. Duration of viral shedding will be calculated for each subject as the number of days (including non-consecutive) determined by qualitative or quantitative RT-PCR to be positive from Day 2 until discharge; means and 95% CIs will be calculated for each group and comparisons will be made.

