3.2.4. Peak and Total Viral Shedding

Viral copies/mL will be estimated as a mean across quantitative RT-PCR replicates. Some replicates may be dropped from the calculations if potential quality control issues are noted. Values below the lower limit of detection will first be imputed as LOD/2 prior to taking the mean of the replicates.

Peak viral shedding will be calculated as the maximum viral concentration (RNA copies/mL) recorded the duration of the inpatient study period for each individual.

Total viral shedding over the inpatient period will be summarized by the area under the curve (AUC), approximated via the linear trapezoidal method, where the trajectory of an individual's viral concentration is

partitioned into $n-1$ subareas until the last inpatient observation at time t_n . As the linear trapezoidal AUC method approximates the entire area by calculating the cumulative sum of the subareas, the formula that will be applied is:

$$AUC_i = \frac{1}{2} * \sum_{j=1}^{n-1} (t_{j+1} - t_j) * (C_{ij+1} + C_{ij})$$

where $(t_{j+1} - t_j)$ is the difference between the j th and $j+1$ th time points within the inpatient period, and C_{ij} and C_{ij+1} are the viral concentrations measured at the j th and $j+1$ th time points for the i th individual. Intermittent missing values are expected to be minimal, so no imputation is planned.

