4.6.1. Clinical Variables

Clinical variables such as viral detection, viral shedding, and solicited symptoms and laboratory findings that are a part of the definition of symptomatic influenza virus infection, are assessed at each study day during the confinement period, after the day of study challenge. Symptoms are also assessed in the clinic visit on Day 15.

Virologic assessments are done at screening (Days -45 to -3), baseline (Days -2 and -1), and then repeated daily from Days 2-8 during the confinement period or for a longer period if still RT-PCR positive for influenza on Days 7 or 8 until two negative swabs are confirmed, at least 12 hours apart, consecutively. Only qualitative RT-PCR is performed at the screening visit, but subsequently nasopharyngeal (NP) swab samples are collected for quantitative RT-PCR as well. Quantitative RT-PCR (qRT-PCR) will be conducted by a research laboratory at Duke University. Qualitative RT-PCR is conducted via multiplex respiratory virus assay (BIOFIRE® FILMARRAY® respiratory panel by bioMérieux or Luminex xTAG®) on NP swabs at the local clinical site. Qualitative and quantitative RT-PCR for influenza from NLF specimens and quantitative viral culture from NP swabs and/or NLF specimens may be performed as well; these would be analyzed subsequently to compilation of the primary CSR, if the assays are performed.

Symptomatic influenza infection is assessed using a Modified Jackson score (MJS) collected by study staff twice a day (approximately 8 AM and after 3 PM) from Day -2 until the time of discharge, and again at the Day 15 visit to assess any ongoing symptoms. [Figure 4](#) displays the MJS investigator tool for assessing symptoms. Fever and lymphopenia, both included among the MJS symptoms for determining the symptomatic influenza attack rate, are assessed separately from the MJS form.

An additional validated, patient-reported outcome (PRO) measure to standardize assessment of influenza symptoms in clinical research (i.e., FLU-PRO Survey Instrument and Validation Diary) is to be completed by participants once a day (after 3:00 PM) from Day -2 through Day 15. The investigators review the FLU-PRO and Validation Diary at the Day 15 visit to assess any ongoing symptoms. The FLU-PRO questionnaire is presented in [Figure 5](#) for reference.

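### The signed-rank test in Protocol 9.5.2 cannot show whether quantitative RT-PCR and quantitative culture are consistent: a constant offset or different detection floors make it reject, and a non-significant result is not agreement

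*Protocol*

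**What the plan says.** Protocol 9.5.2 defines peak shedding and an AUC for each subject and adds: "These will be calculated separately for quantitative RT-PCR and quantitative culture". It then plans a Wilcoxon signed-rank test of these variables "between quantitative RT-PCR and quantitative culture across all subjects, to assess if these methods of viral quantification are consistent". The sentence after that reads: "Scatterplots will also be presented, along with Spearman rank-order correlation estimates". It sets no criterion for consistency, does not say which subjects enter the correlation, and does not say which result decides if the test and the correlation disagree.

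SAP 3.2.4 puts RT-PCR peak shedding in RNA copies/mL and sets values below detection to half the limit of detection. Neither document gives a unit or a below-detection rule for culture. Protocol 8.1.4.1 makes culture optional, and Protocol Section 3 lists it under exploratory objective 13. SAP 4.6.1 says of culture and the nasal-lavage assays: "these would be analyzed subsequently to compilation of the primary CSR, if the assays are performed". The SAP does not repeat the signed-rank comparison and names no replacement. SAP Section 14 reports no substantive change from the analysis planned in the protocol.

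**The concern.** Consistency between two assays can mean that they agree on who is positive, that they rank shedders alike, or that they give the same values once on a common scale. The signed-rank null is none of the first two, and it matches the third only partly: it concerns the centre of the paired differences, not their spread. With no common scale described, rejection may reflect nothing more than a conversion factor or two different floors. Non-rejection may be taken as consistency although it says nothing about association.

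At stake is how a report describes the relation between RNA and culturable virus. A reader could be told that two closely concordant assays are inconsistent.

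**Working it through.** **No plan figure to reproduce.** The documents give no sample size, power or criterion for this comparison.

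**Inputs.** Test, variables and population: Protocol 9.5.2. Level: two-sided 0.05, Protocol 9.5.1. Active subjects, from the cohort sizes in Protocol 6.3.1: at least 12 + 12 + 17 + 17 = 58 (cohorts 1A, 2A, 3A, 3B) and at most 36 + 36 + 34 = 106. Assumed, because the documents do not give them: half of subjects infected, log10 peak SD 1.2 among infected, uninfected subjects set to a floor on each assay, and the size of any offset.

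**Step 1: constant offset, exact.** If RT-PCR = c × culture with c > 1, every difference is positive, on the raw or the log scale, although the rank correlation is 1. The exact two-sided p-value when all n differences share a sign is 2/2^n:
- n = 6: 2/64 = 0.031
- n = 10: 2/1024 = 0.002
- n = 30: 1.9 × 10^-9

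**Step 2: near-perfect concordance, simulated** (r = 0.999 among infected, N = 58 or 106).
- Offset of 0.3, 0.5, 1 or 3 log10: 100% rejected.
- No offset, floors 0.3 log10 apart: 100% rejected. All non-shedders then carry the same non-zero difference, and this alone decides the test.

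**Step 3: no association among infected** (r = 0, equal centres).

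| Setting | Rejected | All-subject Spearman |
|---|---|---|
| Equal floors, every infected subject positive on both assays | about 5% | 0.85 (0.00 among infected) |
| Culture positive in 40% to 80% of infected | 37% to 100% | 0.46 to 0.72 |
| Full positivity agreement, floors 0.3 log10 apart | 61% to 81% | not reported |

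The lower end of the second row varies with simulation error and the assumed floor: a separate 400-trial run with 80% culture positivity gave 31% at N = 58 and 61% at N = 106.

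Without any floor, independent assays with symmetric distributions about the same centre were rejected in 4.3% to 5.4% of replicates (n = 30 to 114), and perfectly inverse assays in 4.7% to 4.9%. Independent assays sharing a median, one of them skewed, were rejected in 26% (n = 62), 42% (n = 106) and 45% (n = 114).

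**Step 4: why the pooled Spearman is high.** Scale ranks to 0–1. The uninfected half is tied at 0.25; the infected half is uniform on 0.5–1, with mean 0.75 and variance 0.5²/12 = 0.0208. Between-group variance is 0.25² = 0.0625. Total variance is 0.0625 + 0.5 × 0.0208 = 0.0729. With no association among infected subjects, rho = 0.0625/0.0729 = 6/7, about 0.86. That value comes entirely from agreement on who is positive.

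**The case against.** The strongest reply is that the plan does not rest on this test alone. The scatterplots would show an offset or a cluster at the floor, and Spearman measures association. Protocol 9.5.1 labels hypothesis tests exploratory and allows other methods if they are stated and justified in the SAP or CSR. This stands as mitigation. It does not settle the matter, because the stated purpose is attached to the signed-rank test, and rho = 1 can sit beside a rejection with no rule for reading the two together.

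A reader might infer that unrelated assays would generally pass as consistent. The documents do not support that. The 5% rejection rate needs the same numerical centre, the same floor and full positive/negative agreement. Two assays in different units would seldom share a centre, and once culture misses some infected subjects the test often rejects. Nor is the test blind to all disagreement: it detects systematic bias.

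A reader might also infer that the pooled correlation is meaningless. It is not: it correctly reflects agreement on positivity, but it mixes that with association among shedders. Finally, different units are documented only for RT-PCR; an infectious-virus unit for culture is an inference, and Step 1 needs only a constant offset.

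**Conclusion.** The point holds as a mismatch between test and stated purpose. Rejection can arise from an offset or from detection floors alone (100% in simulation at 0.3 log10 for either), and non-rejection is not evidence of agreement. The percentages rest on assumed infection rate, spread, offsets and floors; the exact result in Step 1 needs only a constant factor.

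The practical weight is modest. Culture is optional, exploratory and deferred. A reader might infer that a primary endpoint depends on this comparison, but the case definition (Protocol 4.1, SAP 3.2.1) and the escalation rules use RT-PCR and symptoms, and nothing makes the attack rate or the dose choice depend on culture. A reader might also take the SAP to have adopted the test. It has not, but it has not replaced it either, so whoever writes the addendum would start from the protocol wording.

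**What to change.** In Protocol 9.5.2 and the SAP addendum, remove the consistency inference from the signed-rank test and assess consistency by:

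- **Positive/negative agreement by swab-day:** a 2×2 table with percent agreement and kappa, with confidence intervals that allow for repeated swabs within participant, for example a participant-level bootstrap. SAP 7.1.3 already cross-tabulates qualitative against quantitative RT-PCR in a similar way.
- **Association among RT-PCR-positive participants:** Spearman correlation of peak and of AUC with a 95% CI. Report how many are culture-negative, and either treat values below the culture detection limit as censored or show results with and without them.
- **Scale:** state the culture unit and detection limit, and report the mean log10 RNA-to-culture ratio descriptively, not as a test of agreement.

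The cost is wording; the data are the same. The downside is fewer participants and wider intervals in the RT-PCR-positive subset.

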# 4. **STUDY DESIGN**

## 4.1 **Overall Design**

This is an exploratory Phase 1, blinded, randomized, dose-finding influenza virus challenge study in approximately between 62-114 (targeted maximum sample size of 106 active plus 8 shams) males and non-pregnant females, 18 to 45 years old, inclusive, who are in good health and meet all eligibility criteria. The clinical study is designed to determine the optimal infectious dose and safety profile of a recombinant influenza A/Texas/71/2017 (H3N2) clade 3C3a strain in healthy adult volunteers.

The study will enroll approximately between 13-39 subjects in each of up to 3 challenge dose groups at 2 sites (Duke University [DU] and University of Maryland [UMD]) for approximately between 62-114 subjects total for the study. We plan to enroll each challenge dose group according to an adaptive dose-escalation schedule (Figure 1) which allows study results (see Section 9.5.6) to be analyzed between challenge cohorts to inform the sample size and virus dose for the next escalation cohort(s). The study timeline anticipates 4-6 weeks of lead-time for studyspecific screening and start-up activities for the initial cohort, and similarly, 4-6 weeks between subsequent cohorts at each site to evaluate study results and turn-over of the clinical unit. However, to compress the overall dosing timelines, challenge cohorts may be performed concurrently or around a 2-week timeline between the sites. We plan up to 2 weeks (Day -2 to Day 8) to complete the clinical in-patient component for each challenge cohort, thus altogether projecting the following to complete the dose-ranging clinical confinement component: up to 3.5 to 4 months, if 3 challenge cohorts evaluated; 4 to 4.5 months, if 4 challenge cohorts evaluated; 5 to 6 months if 5 challenge cohorts evaluated; and 5.5 to 6.5 months if 6 challenge cohorts evaluated. Each participant has an additional 7 weeks of follow-up post confinement. The study period could range from approximately 7.5 months to one year, depending upon the number of challenge cohorts enrolled.

Potentially eligible study subjects may be pre-screened under an active screening protocol (DMID 20-0004) to identify those with HAI antibody titers  $\leq$ 1:40 specific to the challenge virus strain.

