Solicited influenza symptoms will be presented by the frequency and percentage of subjects reporting each symptom, severity, day, and challenge dose group. The self-reported (FLU-PRO) and investigator-assessed symptoms will be tabulated separately. Total symptom scores will be computed for each subject and each scoring algorithm. Mean scores for both algorithms will be calculated for each group, along with 95% CI, and the groups will be compared as described in Section 9.5.1. Additionally, the number and percentage of subjects meeting each scale's definition of symptomatic and asymptomatic will be cross-tabulated by challenge dose group. A Wilcoxon rank-sum test will be used to compare the distributions of each set of scores, across all subjects that received active challenge, to determine the agreement between the two symptom reporting methods.

Clinical endpoints (including the primary endpoints) will be assessed in the ITT population. Subjects who withdraw during the challenge period prior to meeting discharge criteria will be included in summaries where data are available. Subjects who withdraw during the challenge period and have yet to meet the relevant clinical case definition will be excluded from analyses of aggregate endpoints such as the incidence of symptomatic influenza.

If at least 10% of the analysis data would be dropped according to PP population exclusions described in Section 9.4, the PP population will be used as a sensitivity analysis for the primary ITT analysis.

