3.2.5. Symptom Scores

The cumulative Modified Jackson Score (MJS; see [Figure 4](#)) will be calculated as described in [Section 3.2.1](#).

The area under the MJS curve will be calculated for each participant from Day 2 through Day 8, for uninfected participants (see [Section 3.2.3](#)), or from the first RT-PCR+ day through the last, for infected participants; this calculation will be made as described above in [Section 3.2.4](#) for total viral shedding, except in this case scaled by the number of days over which symptoms are summed.

The FLU-PRO total severity score is defined as the mean score across all 32 items (see [Figure 5](#)), with component scores ranging from 0 to 4. Six domain scores are also computed as mean scores, representing symptom severity in each body system. Scores will be computed for each study day utilizing the maximum severity score per symptom, and cumulative FLU-PRO scores (for the total FLU-PRO score and component scores) will be computed as the sum of the daily scores over the relevant time period.

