7.2. Exploratory Clinical Analyses

7.2.1. Comparisons of MJS to FLU-PRO

Total FLU-PRO scores will be presented by study day and challenge group in [Figure 11](#), with RT-PCR+ study days annotated on the heatmap, for comparison to [Figure 10](#) for MJS scores.

FLU-PRO symptoms will be summarized by study day for currently infected participants (similarly to MJS symptoms in [Table 19](#) through [Table 22](#)) in [Table 37](#) through [Table 40](#), for a qualitative comparison between the two symptom scoring tools. The maximum severities of symptoms reported during the challenge period will be cross-tabulated between MJS and FLU-PRO in [Table 41](#) (infected participants) and [Table 42](#) (uninfected participants). Cumulative FLU-PRO scores will be summarized by challenge dose group and infection status in [Table 43](#), with maximum cumulative MJS scores (already analyzed as part of the primary endpoint in [Table 14](#)) included for reference.

Scatterplots of each symptom score by total viral shedding (log-10 AUC) will be presented in [Figure 12](#), along with Spearman rank correlation coefficient estimates between each score and the area under the viral shedding curve. Mean total MJS and FLU-PRO scores will be presented by challenge dose group, viral shedding status, and study day during the challenge period, in [Figure 13](#); the entire distributions of symptom scores will be presented in boxplots in [Figure 14](#).

FLU-PRO symptoms will be detailed in [Listing 9](#), and answers to additional FLU-PRO questions will be presented in [Listing 10](#).

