13. TECHNICAL DETAILS

SAS version 9.4 or above, or R version 4.2 or above, will be used to generate all tables, figures and listings.

**14. SUMMARY OF CHANGES IN THE CONDUCT OF THE STUDY OR
PLANNED ANALYSES**

No substantive changes to the analysis planned in the protocol have been made.

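### The protocol's rank-sum test cannot measure agreement between MJS and FLU-PRO; the SAP drops it without saying so and adds no within-participant statistic for the two totals

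*Protocol*

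**What the plan says.** Protocol 9.5.2 first sets the unit of data: "Total symptom scores will be computed for each subject and each scoring algorithm". It then specifies the comparison: "A Wilcoxon rank-sum test will be used to compare the distributions of each set of scores". The sample is "across all subjects that received active challenge" and the stated purpose is "to determine the agreement between the two symptom reporting methods".

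Two other protocol passages matter. In the same section, the comparison of quantitative RT-PCR with quantitative culture, also two methods on the same subjects, gets a signed-rank test, scatterplots and Spearman estimates. Section 9.5.1 undertakes that any approach other than those listed will be stated and justified in the SAP and/or the CSR.

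In the SAP, Section 3.2.1 builds MJS as a sum of items graded 0 to 3. Section 3.2.5 defines the other instrument differently: "The FLU-PRO total severity score is defined as the mean score across all 32 items", with items from 0 to 4 and daily scores summed over days.

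SAP 7.2.1, the section on comparing the instruments, does not mention the rank-sum test. It plans:

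- daily total-score heatmaps (Figures 10-11), mean totals by day (Figure 13) and boxplots (Figure 14);
- symptom-level cross-tabulations, with an any-symptom block (Tables 41-42);
- group summaries of both cumulative scores (Table 43);
- scatterplots of each score against viral shedding (Figure 12), "along with Spearman rank correlation coefficient estimates between each score and the area under the viral shedding curve".

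SAP Section 14 states: "No substantive changes to the analysis planned in the protocol have been made".

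**The concern.** Agreement is a property of pairs: does a participant who scores high on one instrument score high on the other? A rank-sum test treats the two columns as independent samples and asks whether one tends to be larger. That ignores the pairing. Because one score is a sum and the other a mean, it also mainly detects the difference in units.

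The SAP leaves the question open in a different way. The test has gone, but nothing planned replaces it at the level of total scores, and nothing says it was withdrawn. A reader holding both documents cannot tell whether the test stands. What is at stake is the exploratory question of whether the self-reported FLU-PRO tracks the investigator-collected MJS.

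**Working it through.** The documents give no sample size, power or critical value for this comparison, so there is no planned figure to reproduce.

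**Number of participants.** Protocol 4.1 gives a "targeted maximum sample size of 106 active plus 8 shams": 3 × 12 + 3 × 12 + 2 × 17 = 106 active. The lower end of its stated range, 62 in total, is 12 + 12 + 34 = 58 active plus 4 shams. The pooled test would therefore use 58 to 106 people.

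**Scales.** The case definition lists 14 signs and symptoms; fever and feverish contribute once (SAP 3.2.1), leaving 13.

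- MJS daily maximum: 13 × 3 = 39 on Days 2, 4 and 8, when lymphocytes are scheduled, and 12 × 3 = 36 otherwise.
- MJS five-day maximum: 2 × 39 + 3 × 36 = 186 for Days 2-6 or Days 4-8.
- FLU-PRO: 0 to 4 a day, so 7 × 4 = 28 over Days 2-8.

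**Why pairing cannot matter.** Pool the 2n scores and rank them. With W the sum of the MJS ranks, U = W - n(n+1)/2. W depends only on the two sets of values, so re-pairing them leaves U and p unchanged.

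**Exact check, n = 106.** One simulated set of MJS totals and one of FLU-PRO totals, paired three ways (U would be expected at 106 × 106 / 2 = 5618 if the distributions were equal):

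| Pairing | Spearman | U | p |
|---|---|---|---|
| Perfect | 1.00 | 7968.5 | 1.05e-07 |
| Shuffled | 0.13 | 7968.5 | 1.05e-07 |
| Reversed | -0.98 | 7968.5 | 1.05e-07 |

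**Repeated sampling.** The documents do not give the score distributions. The assumptions are: 10% to 70% of participants score zero; non-zero scores are gamma-distributed, averaging 8% of the scale maximum; FLU-PRO runs 0-28; MJS runs 0-195 (13 × 3 × 5, slightly above the 186 attainable on scheduled laboratory days). Perfect agreement means FLU-PRO is an exact rescaling of the same person's MJS. No agreement means an independent draw. There were 500 replicates per cell, two-sided 5%. Rank-sum rejection rates:

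| n | Scoring zero | Perfect agreement | No agreement |
|---|---|---|---|
| 106 | 10% | 1.00 | 1.00 |
| 106 | 30% | 1.00 | 1.00 |
| 106 | 50% | 0.95 | 0.77 |
| 106 | 70% | 0.004 | 0.19 |
| 58 | 10% | 1.00 | 1.00 |
| 58 | 30% | 0.998 | 0.966 |
| 58 | 50% | 0.53 | 0.51 |
| 58 | 70% | 0.002 | 0.13 |

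Rejection follows the share of zeros and the units, not agreement.

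**Alternatives checked.**

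- Both scores on a common scale: rejection is 0% under perfect agreement and about 3% to 6% under none, so non-significance does not show agreement.
- Signed-rank on raw totals: 100% rejection under both conditions with 10% or 30% zeros, at n = 58 and n = 106.
- Spearman between each participant's two totals: mean 1.00 under perfect agreement and about 0.00 under none. For an assumed true value of 0.8, the Fisher z interval, tanh(1.099 ± 1.96/√(n - 3)), is 0.72 to 0.86 at n = 106 and 0.68 to 0.88 at n = 58.

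**The case against.** The strongest reply is that the SAP is the operative plan. The protocol leaves detail to it, it says it describes all planned analyses, and it has no rank-sum test. That stands. A reader might infer that the trial will publish a tiny p-value and conclude that the instruments disagree whatever the data show. The documents do not support this: the SAP does not plan the test, and rejection is not assured when half or more of participants score zero.

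A reader might also infer that the SAP offers only symptom-level cross-tabulations. It does not: Table 43 and Figures 10-14 display total scores, and the any-symptom block of Tables 41-42 crosses each person's maximum severity on the two tools. What is missing is narrower, namely a statistic relating a participant's two totals.

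The definition of FLU-PRO as a 32-item mean comes from the SAP, whereas the protocol speaks only of totals. This does not rescue the test. Summing the items instead gives up to 32 × 4 × 7 = 896 over seven days, still a different unit, and with 10% zeros the test again rejected in every replicate under both conditions.

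Two further points stand in part. Spearman measures monotone association, not strict agreement, so it should be labelled that way. And whether dropping one exploratory test is substantive is arguable, and the CSR could still explain it. But Protocol 9.5.1 asks for a stated justification, and Section 14 is the natural place for one.

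**Conclusion.** The point holds in limited form. The protocol names a test that cannot answer its stated question. The SAP omits it without a record and plans no within-participant statistic for the two totals.

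The invariance to pairing is exact and needs no assumption. The simulated rejection rates rest on assumed score distributions and only illustrate how the test would behave.

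A reader might infer that the primary result is at risk, since the test sits in the protocol's primary-endpoint section. It is not. Protocol 4.1 and SAP 7.2 treat the instrument comparison as exploratory, the endpoints under primary objective 3 use MJS alone, and the attack rate, escalation and optimal dose use MJS with RT-PCR. It should be corrected because the correction is cheap, not because a dose conclusion depends on it.

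**What to change.** 1. In SAP Section 14, record that the protocol's rank-sum comparison of MJS and FLU-PRO is withdrawn, and why: the scores are paired and have no common unit.
2. In SAP 7.2.1, add a scatterplot with one point per actively challenged participant, cumulative MJS against cumulative FLU-PRO summed over the same days (for example Days 2-8), with the Spearman correlation and its 95% CI. Describe it as association between the instruments.
3. Define the matched-day scores. The scores now planned do not match: MJS is the maximum over a five-day window, while Table 43 sums FLU-PRO over the whole challenge period, which can run past Day 8. State whether fever and lymphopenia, which are not on the MJS form, are included.
4. Do not substitute a signed-rank test on raw totals.

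The cost is one matched-day derived score, one plot and one statistic. Both instruments are already scheduled daily on Days 2-8, so no new data are needed.
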